1.2. Study Design

Study EZCB is a Phase 2, randomized, double-blind, placebo-controlled, parallel-arm study to investigate the efficacy and safety of LY3561774 in adults with mixed dyslipidemia.

Participants will be randomly assigned in a 2:1:2:2 ratio to placebo: LY3561774 100 mg:400 mg:800 mg. Placebo participants will be randomly assigned such that each dose cohort will have a matching placebo cohort that receives the same dose volume to maintain the study blind.

Participants will be stratified according to the Visit 1 TG level of less than 250 mg/dL and 250 mg/dL or greater.

Study intervention administration is by subcutaneous injection. Dosing will occur twice during the study, on Day 0 and Day 90 ± 5 days.

If a participant's ApoB levels do not return to 80% of baseline or higher on Day 270, then the participant will continue to the follow-up visit at Day 360.

If a participant's ApoB levels return to ≥80% of baseline or higher on Day 270, then Day 270 is the participant's last study visit.

Figure EZCB.1.1 illustrates the study schema.

2. Statistical Hypotheses

The Study EZCB hypothesis for the primary objective is that at least one dose of LY3561774 100 mg, 400 mg, or 800 mg is superior in percent change from baseline for ApoB relative to placebo at Day 180 in participants with mixed dyslipidemia.

Thus, the null hypothesis to be tested in relation to the primary estimand is that LY3561774 100 mg, 400 mg and 800 mg are not different from placebo with respect to percent change in ApoB from baseline to Day 180.

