2.1. Multiplicity Adjustment

All treatment comparisons will be performed at the full significance level of 0.05. No adjustment for multiplicity will be performed.

3. Analysis Sets

This table defines the analysis population and datasets for the purposes of analysis.

Population	Description
Screened	All participants who signed informed consent.
Randomized	All participants who are randomly assigned to a treatment arm.
EAS	Data obtained during the treatment period from all randomly assigned participants who are exposed to at least 1 dose of the study intervention and are not discontinued due to inadvertent enrollment. Excludes data after any of
	 permanent discontinuation of intervention initiation of excluded medications taken during the study, and new initiation of any lipid-lowering drug required to be on a stable regimen prior to treatment per the protocol inclusion criteria.
	Participants will be included in the treatment group to which they were randomly assigned.
FAS	Data obtained during the treatment period from all randomly assigned participants who are exposed to at least 1 dose of study intervention, regardless of adherence to intervention, and are not discontinued due to inadvertent enrollment. Participants will be included in the treatment group to which they were randomly assigned.
SAS	Data obtained during the treatment period plus safety follow-up from all randomly assigned participants who are exposed to at least 1 dose of the study intervention, regardless of adherence to the intervention, and are not discontinued due to inadvertent enrollment. Participants will be included in the treatment group to which they were randomly assigned.

Abbreviations: EAS = efficacy analysis set; FAS = full analysis set; SAS = safety analysis set.

4. Statistical Analyses

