4.3.1. Definition of Endpoint

The primary efficacy comparison will be based on the contrast between each treatment group of LY3561774 and placebo for the mean percent change of ApoB between randomization at Visit 2 and Day 180.

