4.3.2. Main Analytical Approach

Mean percent change of ApoB will be analyzed using the MMRM model for the efficacy estimand. As described in Section 4.1, the response variable will be log-transformed.

A restricted maximum likelihood-based MMRM analysis will be used to analyze continuous longitudinal variables. All longitudinal observations taken at each scheduled postbaseline visit will be included in the analysis. The model for the analysis of the primary efficacy endpoint of percent change from baseline in ApoB will include the fixed class effects of treatment group (placebo, LY3561774 100 mg, LY3561774 400 mg, and LY3561774 800 mg), visit, treatment-by-visit interaction, Visit 1 TG stratum (lower than 250 mg/dL, 250 mg/dL or greater) as well as the continuous baseline value of the log-transformed dependent variable.

An unstructured covariance structure will be used to model the within-participant errors. Significance tests will be based on LS means and type III tests. If this analysis fails to converge, these covariance structures will be tested in order

- Toeplitz with heterogeneity
- autoregressive with heterogeneity
- compound symmetry with heterogeneous variances
- Toeplitz
- · autoregressive, and
- compound symmetry without heterogeneous variances.

The first covariance structure that converges will be used. The Kenward-Roger approximation will be used to estimate denominator degrees of freedom.

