4.5.1. Analyses using the Efficacy Analysis Set

These two exploratory study objectives will be analyzed using the EAS and the associated efficacy estimand.

Percent change from baseline at Day 180 for

- high-sensitivity C-reactive protein (hsCRP)
- apolipoprotein A-I (ApoA-I)
- apolipoprotein C-III (ApoC-III)
- VLDL-C
- urine albumin/creatinine ratio (UACR)
- hemoglobin A1c (HbA1c), and
- fasting glucose (FG).

Percent change from baseline in time-averaged parameters over Days 30 to 180 and Days 120 to 270 for

- non-HDL-C
- LDL-C
- HDL-C
- ApoB, and
- TG.

These endpoints will be analyzed using the MMRM modeling strategy as detailed in Section 4.3.2. Comparisons of difference in time-averaged response from baseline for treatment group k versus placebo reference group, indexed by R, will be made by using contrasts of LS means to calculate

$$\hat{\theta}_{\Delta k} = \hat{\mu}_{1k} - \hat{\mu}_{1R} + \sum_{t} w_t \left(\hat{\beta}_{k:t} - \hat{\beta}_{R:t} \right),$$

where $\hat{\mu}_{1k}$ is the coefficient corresponding to treatment group k, $\hat{\beta}_{k:t}$ corresponds to the treatment-time interaction coefficient, R represents the placebo reference group, and w_t is the weight at time t informed by the trapezoidal rule. Estimates and CIs will be constructed from the model-based versions using the delta method. An overall test of significance will be conducted using the F-test under the null hypothesis that $\theta_{\Delta k}=0$ for all LY3561774 arms simultaneously.

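### Does the joint Day 180 null in SAP Section 2 need an overall test of its own?

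*SAP*

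**What the plan says.** SAP Section 2 states the primary hypothesis as "at least one dose of LY3561774 100 mg, 400 mg, or 800 mg is superior in percent change from baseline for ApoB" at Day 180. From it the section derives "the null hypothesis to be tested in relation to the primary estimand", namely that "LY3561774 100 mg, 400 mg and 800 mg are not different from placebo with respect to percent change in ApoB". That is one null over three doses.

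The analysis sections work dose by dose. SAP 4.3.1: "The primary efficacy comparison will be based on the contrast between each treatment group of LY3561774 and placebo". SAP 2.1: "All treatment comparisons will be performed at the full significance level of 0.05. No adjustment for multiplicity will be performed". Protocol 9.3.2 likewise sets each active group against placebo at the full 0.05. The population summary for the primary estimand in SAP 1.1 is also a difference for each dose. SAP 4.3.2 adds, for the primary MMRM, "Significance tests will be based on LS means and type III tests".

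The one overall test that the SAP writes out is in SAP 4.5.1, for exploratory time-averaged lipids: "An overall test of significance will be conducted using the F-test under the null hypothesis that" the time-averaged difference is zero "for all LY3561774 arms simultaneously".

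**The concern.** A null described as the one to be tested should have a test, or at least a decision rule. Here it has three contrasts and no sentence linking them to it. An exploratory endpoint has an explicit overall F-test and the primary endpoint does not, which looks like an oversight.

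The type III tests in SAP 4.3.2 do not supply the link. With treatment, visit and their interaction in the model, the type III treatment test concerns the average over the postbaseline visits, and the interaction test concerns whether the profiles are parallel. Neither is the Day 180 null.

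At stake would be a choice made after the data are seen, between declaring success on any significant dose and declaring it on an overall test. The two can disagree, and they have different error rates for the study-level claim.

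**Working it through.** **Inputs.** Protocol 9.5 and SAP Section 5 give about 175 participants in a 2:1:2:2 ratio, SD 15%, two-sided alpha 0.05, a -30% difference and power above 99%. The 20% dropout is in Protocol 9.5. Completers:

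- Placebo, 400 mg and 800 mg: 175 × 2/7 × 0.8 = 40 each.
- 100 mg: 175 × 1/7 × 0.8 = 20.

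**The plan's own figure.** The noncentrality of one contrast is 30 / [15 × √(1/n₁ + 1/n₂)].

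- 40 v 40: 30/3.354 = 8.94.
- 40 v 20: 30/4.108 = 7.30.

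Both give power above 99.99%, so the stated >99% reproduces. It is a pairwise calculation, in keeping with per-dose testing.

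**Two rules for the joint null.** I used a one-way layout on completers with 140 - 4 = 136 df as an approximation to the Day 180 MMRM contrasts. The critical values are t = 1.978 and F(3,136) = 2.671.

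Under the joint null (2 million simulated trials):

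| Result | Share of trials |
|---|---|
| Any dose significant, two-sided | 12.8% |
| Any dose significant in the benefit direction | 6.4% |
| F-test significant | 5.0% |
| Any dose significant, F-test not | 8.7% |
| F-test significant, no dose | 0.8% |

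Three independent tests would give 1 - 0.95³ = 14.3%. The shared placebo arm lowers this to 12.8%.

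F-test power uses the noncentrality λ = Σ nᵢ(μᵢ - μ̄)²/15²:

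- All doses at -30: μ̄ = -30 × 100/140 = -21.43; λ = (40 × 21.43² + 100 × 8.57²)/225 = 114.3; power >99.99%.
- 100/400/800 mg at -5/-10/-10 (assumed): μ̄ = -900/140 = -6.43; λ = 12.06; power 83.1%.
- At 0/0/-10 (assumed): μ̄ = -400/140 = -2.86; λ = 12.70; power 85.1%.

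**What adding the F-test would do.** Suppose the at-least-one-dose claim required a significant F-test and a dose significant in the benefit direction:

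| Assumed effects, 100/400/800 mg | Any dose in benefit direction | F-test and such a dose |
|---|---|---|
| -5/-10/-10% | 93.9% | 82.8% |
| 0/0/-10% | 84.2% | 78.4% |

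The gaps, 93.9 - 82.8 = 11.1 and 84.2 - 78.4 = 5.8 points, are trials in which a dose is shown superior at 0.05 while the report may not conclude that at least one dose is superior.

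**Reading the sections together.** The alternative is that some dose is superior, and the null is that no dose differs. The contrasts that could show a dose superior are listed in SAP 4.3.1. Their level is fixed in SAP 2.1, which is a subsection of the hypotheses section itself. An alternative of that form is established when one of its components is established. Protocol 9.1 joins the three doses with an *or*, which fits the same reading.

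**The case for a change.** The best case for a change runs as follows. SAP 2.1 fixes the level of each comparison; it does not state what rejects the null of Section 2. If any significant dose is enough, that null is tested at about 12.8%, a rate the SAP never gives. If an overall test was meant, it is missing. The type III treatment test is a poor stand-in. Take an assumed -10% in every dose through Day 150 and nothing from Day 180. The mean effect over ten visits is -10 × 6/10 = -6, and with a between-visit correlation of 0.5 to 0.7 the test rejects in 66% to 52% of trials although the Day 180 null is true. The plan also allows up to three unblinded interim analyses, so the rule should be settled early. A sentence would do it.

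Much of this stands: the linking sentence is absent, the type III point is correct in principle, and the figures are right. Three things limit it.

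- The 12.8% is the arithmetic consequence of testing three doses unadjusted, which the SAP and protocol both declare. It is not a separate defect.
- The room for a later choice is small. The per-dose contrasts are the only Day 180 tests of dose against placebo on paper, so relying on an overall Day 180 F-test would be a visible departure from the SAP. An F-test for an exploratory endpoint creates no duty to run one for the primary.
- The type III scenario is hypothetical. Protocol 2.2 reports the Phase 1 effect lasting to the final collection at Day 169, and SAP 4.3.1 bases the primary comparison on the per-dose contrasts.

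**Conclusion.** No change follows. SAP Section 2 omits the sentence that ties its joint null to a decision rule. An analyst following SAP 2.1 and 4.3.1 supplies the rule without difficulty: any significant per-dose contrast rejects it, with no adjustment. Whichever way Section 2 is read, the three Day 180 estimates, intervals and p-values are identical, each test keeps its own 0.05, and these are what a Phase 2 study meant to inform dose decisions will use. Rewording the section would alter no result.

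An added F-test is a trade-off and not a correction. It would hold the joint null at 5.0% instead of about 12.8%, protection the sponsor has openly declined. The price is 11.1 or 5.8 points of chance to make the claim at the two assumed smaller effect patterns, and reports that can contradict themselves. At the planned -30% the two rules give the same answer almost surely.

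These figures assume SD 15%, 40/20/40/40 completers and a one-way approximation on the percent scale; the actual model is a log-scale MMRM. Effects other than -30% are assumptions. A reader of the report should take the p-values as per comparison, and treat a claim that at least one dose works as carrying a false-positive rate of about 6.4% in the benefit direction.

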2.1. Multiplicity Adjustment

All treatment comparisons will be performed at the full significance level of 0.05. No adjustment for multiplicity will be performed.

3. Analysis Sets

This table defines the analysis population and datasets for the purposes of analysis.

Population	Description
Screened	All participants who signed informed consent.
Randomized	All participants who are randomly assigned to a treatment arm.
EAS	Data obtained during the treatment period from all randomly assigned participants who are exposed to at least 1 dose of the study intervention and are not discontinued due to inadvertent enrollment. Excludes data after any of
	 permanent discontinuation of intervention initiation of excluded medications taken during the study, and new initiation of any lipid-lowering drug required to be on a stable regimen prior to treatment per the protocol inclusion criteria.
	Participants will be included in the treatment group to which they were randomly assigned.
FAS	Data obtained during the treatment period from all randomly assigned participants who are exposed to at least 1 dose of study intervention, regardless of adherence to intervention, and are not discontinued due to inadvertent enrollment. Participants will be included in the treatment group to which they were randomly assigned.
SAS	Data obtained during the treatment period plus safety follow-up from all randomly assigned participants who are exposed to at least 1 dose of the study intervention, regardless of adherence to the intervention, and are not discontinued due to inadvertent enrollment. Participants will be included in the treatment group to which they were randomly assigned.

Abbreviations: EAS = efficacy analysis set; FAS = full analysis set; SAS = safety analysis set.

4. Statistical Analyses

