7.1. Discontinuation of Study Intervention

When necessary, a participant may be permanently discontinued from study intervention.

Situations when discontinuation of study intervention may occur

A participant should be permanently discontinued from study intervention if

- the participant becomes pregnant during the study
- a prohibited treatment listed in Section 10.7.3 is initiated during the study, or
- in the opinion of the investigator, the participant should permanently discontinue the study intervention for safety reasons.

If the investigator determines that a systemic hypersensitivity reaction has occurred related to study intervention administration, the participant may be permanently discontinued from the study intervention, and the sponsor's designated medical monitor should be notified. If the investigator is uncertain about whether a systemic hypersensitivity reaction has occurred and whether discontinuation of study intervention is warranted, the investigator should consult the sponsor.

If study intervention is permanently discontinued, the participant will remain in the study and follow procedures for the remaining study visits as shown in the SoA.

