9.2. Analyses Sets

This table defines the analysis population and datasets for the purposes of analysis.

Population	Description
Screened	All participants who signed informed consent.
Randomized	All participants who are randomly assigned to a treatment arm.
Efficacy Analysis Set (EAS)	Data obtained during the treatment period from all randomly assigned participants who are exposed to at least 1 dose of intervention. Excludes data after permanent discontinuation of intervention. Participants will be included in the treatment group to which they were randomly assigned.
Full Analysis Set (FAS)	Data obtained during the treatment period from all randomly assigned participants who are exposed to at least 1 dose of intervention, regardless of adherence to intervention. Participants will be included in the treatment group to which they were randomly assigned.
Safety Analysis Set (SS)	Data obtained during the treatment period plus safety follow-up from all randomly assigned participants who are exposed to at least 1 dose of intervention, regardless of adherence to intervention. Participants will be included in the treatment group to which they were randomly assigned.

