The clinical question of interest is: what is the treatment difference in key lipid parameters after 180 days of treatment in participants who meet the inclusion criteria regardless of treatment discontinuation?

The treatment-regimen estimand is described by the attributes

- population: participants who were randomized and had at least one dose of study medication; further details can be found in Sections 5 and 9 of the Study EZCB protocol
- endpoint: percent change from baseline in key lipid parameters (low-density lipoprotein-cholesterol [LDL-C], non-high-density lipoprotein-cholesterol [non-HDL-C], high-density lipoprotein-cholesterol [HDL-C], triglycerides [TG], and ApoB) at Day 180, and
- treatment condition: the randomized treatment, regardless of treatment discontinuation.

The intercurrent events are handled by the treatment policy strategy where the potential outcome of interest is the response in the efficacy measurement regardless of treatment adherence.

The potential outcomes related to the treatment-regimen estimand are summarized at the population level using the difference in mean percent changes in key lipid parameters at Day 180 between each dose of LY3561774 and placebo.

The rationale for this estimand is to facilitate analysis based on the real-world scenario (that is, the intention-to-treat principle) for key lipid parameters (LDL-C, non-HDL-C, HDL-C, TG, and ApoB).

Unless otherwise specified, safety assessments will be guided by an estimand comparing the safety of LY3561774 doses with placebo irrespective of adherence to study intervention, including data collected during the treatment period and safety follow-up (that is, the treatment-regimen estimand).

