4.2. Participant Dispositions

A listing and summary of Study EZCB participant disposition for all randomly assigned participants will be provided at the primary and final database locks, respectively. Frequency counts and percentages of all participants screened, randomly assigned, and receiving at least 1 dose of study drug will be presented by treatment groups. A listing and summary of randomly assigned participants not receiving the study drug will be provided. All participants who discontinue Study EZCB and/or the study drug will be identified, and the extent of their participation in Study EZCB will be reported. If known, a reason for their discontinuation will be given. The primary reasons for discontinuation will be listed and summarized by treatment groups.

Details about participant dispositions are included in the appendices: the demographic and baseline characteristics (Appendix 1, Section 6.1), historical illnesses and preexisting conditions (Appendix 2, Section 6.2), treatment compliance (Appendix 3, Section 6.3), concomitant medications (Appendix 4, Section 6.4), and important protocol deviations (Appendix 5, Section 6.5).

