4.6.3. Patient Narratives

Patient narratives contain patient level data and a summary paragraph. Patient narratives will be provided for participants in the randomized population with at least one notable event. Notable events include death, serious adverse events, and permanent discontinuation of study treatment due to an adverse event.

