4.9. Changes to Protocol-Planned Analyses

The description of the EAS was amended to exclude participants who experienced permanent discontinuation of intervention, initiation of excluded medications taken during the study, and new initiation of any lipid-lowering drug required to be on a stable regimen prior to treatment per the Study EZCB protocol inclusion criteria. In the Study EZCB protocol, the EAS was described as only excluding measurements based on permanent discontinuation of intervention. This change is intended to align the analyses based on the EAS with the description of the primary estimand, based on the hypothetical strategy.

For the exploratory analysis of time-averaged endpoints, the days of time-averaging have been augmented from Day 120 to Day 180 to Day 30 to Day 180, and from Day 210 to Day 270 to Day 120 to Day 270. The purpose of this change is to capture a broader measure of effectiveness over time to accompany our other analyses at specific time points.

5. Sample Size Determination

The sample size calculation is based on the primary efficacy estimand and its endpoint, percent change, from baseline at Day 180 in ApoB.

Approximately 175 participants will be randomly assigned in a 2:1:2:2 ratio to placebo: LY3561774 100 mg:400 mg:800 mg. Assuming a dropout rate, this results in approximately 20 completers for the 100 mg group and 40 completers per arm for the rest of the groups.

Assuming a standard deviation of 15%, and a 2-sided alpha level of 0.05, the completers for each treatment arm will provide greater than 99% power to detect a treatment difference of -30% for the primary endpoint.

6. Supporting Documentation

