Participants with elevated or low values meeting specified levels	Excludes analytes collected qualitatively. Definitions provided in Table 59 and 60 from FDA's Standard Safety Tables and Figures Integrated Guide will be used for the numerator ^b . Includes participants with at least 1 postbaseline measurement. For initial controlled analysis sets, maximum baseline is used for elevated assessments and minimum baseline is used for low assessments. For LY-treated analysis sets (all participants receiving at least 1 dose of LY3561774), participants randomly assigned to placebo or active comparator in the initial period, last baseline is used for any change calculations.	FAS
	For controlled analysis sets, statistical comparisons (using methods described in Section 4.3.2) will be included. See Table 24 from FDA's Standard Safety Tables and Figures Integrated Guide (FDA 2022).	
Listing of abnormal laboratory findings	Includes laboratory analytes collected quantitatively (high or low during postbaseline using Level 2 definitions) and qualitatively (abnormal during postbaseline).	FAS

Analysis Type	Analysis Details	Population/Analysis
		Set
	Includes participant identification, treatment group, laboratory analyte collection day (that is, days	
	from start of study intervention), analyte name, and analyte finding.	

Abbreviations: ANCOVA = analysis of covariance; FAS = full analysis set; MMRM = mixed model repeated measures; SD = standard deviation.

- a [PHUSE]. Safety Analytics Working Group. Analyses and displays associated with laboratory analyte measurements in phase 2-4 clinical trials and integrated submission documents update to recommendations. Accessed March 05, 2023. https://phuse.s3.eu-central-1.amazonaws.com/Deliverables/Safety+Analytics/WP068.pdf
- b [FDA] United States Food and Drug Administration. Standard safety tables and figures: integrated guide. August 2022. Accessed May 31, 2023. https://downloads.regulations.gov/FDA-2022-N-1961-0046/attachment_1.pdf

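### The SAP's safety set drops dosed participants discontinued for inadvertent enrollment; the protocol's safety set keeps them, and SAP 4.9 does not declare the change

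*SAP*

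**What the plan says.** Protocol 9.2 defines the safety set (SS) as treatment-period data "plus safety follow-up from all randomly assigned participants who are exposed to at least 1 dose of intervention, regardless of adherence to intervention". It has no eligibility condition.

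SAP Section 3 keeps that structure for its safety analysis set (SAS) but adds one: "regardless of adherence to the intervention, and are not discontinued due to inadvertent enrollment". The EAS and FAS definitions in the same table carry the same condition. The SAP states that it is based on protocol amendment (e), the protocol version reviewed here.

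SAP 4.1 and 4.6 run the safety analyses on the SAS, irrespective of adherence. Appendix 7 assigns its laboratory outputs, including the row "Participants with elevated or low values meeting specified levels", to the FAS.

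SAP 4.9 declares two changes to protocol-planned analyses. One concerns intercurrent events: "The description of the EAS was amended to exclude participants who experienced permanent discontinuation of intervention" (and the two medication events). The other widens the time-averaging windows. Inadvertent enrollment, the SAS and the FAS are not mentioned.

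Two outputs do not depend on the SAS. SAP 4.6.3 says "Patient narratives will be provided for participants in the randomized population with at least one notable event", and SAP 4.2 says "A listing and summary of Study EZCB participant disposition for all randomly assigned participants will be provided".

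**The concern.** A safety set should contain everyone exposed, and the protocol says this one does. Under the SAP's rule, a dosed participant who is later found ineligible and discontinued for that reason drops out of the safety tables. What is lost is that participant's non-serious treatment-emergent events, liver-test and other laboratory elevations, and place in the numerators, denominators and Fisher comparisons. An SAE could be narrated yet missing from the SAE count.

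This touches declared objectives: TEAE frequency, and the incidence of TEAEs, SAEs and discontinuations due to AEs, are secondary endpoints. It also touches a named risk. Protocol 2.3.1 lists hepatobiliary events as a potential risk, and the abnormal liver-test categories and liver-injury screening displays in SAP Table EZCB.4.5 all use the SAS.

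The clause also cannot be applied consistently as written. The SAP does not say what counts as inadvertent enrollment, whether the discontinuation is from intervention or from the study, or when the affected participants are to be identified relative to unblinding.

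**Working it through.** **1. Membership, side by side**

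| Set | Protocol 9.2 | SAP Section 3 | Declared in SAP 4.9? |
|---|---|---|---|
| Safety (SS / SAS) | Randomized, at least 1 dose | Same, minus those discontinued for inadvertent enrollment | No |
| FAS | Randomized, at least 1 dose | Same exclusion added | No |
| EAS | Randomized, at least 1 dose; data after permanent discontinuation of intervention dropped | Same exclusion added, plus two further intercurrent events | Intercurrent events only |

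Only participants *discontinued* for this reason are removed. Someone wrongly enrolled who continues stays in the SAS.

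**2. What discontinued could mean**

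- From intervention: Protocol 7.1 says "the participant will remain in the study and follow procedures for the remaining study visits as shown in the SoA". Safety data would then be collected after dosing and left out of the tables.
- From the study: Protocol 7.2 provides an early discontinuation visit and any applicable follow-up. Less data is collected, but what exists is still excluded.

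Neither section names inadvertent enrollment as a reason.

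**3. The plan's own figures**

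Inputs from Protocol 9.5: 175 randomized 2:1:2:2, 20% dropout, SD 15%, difference −30%, two-sided alpha 0.05.

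- Arms: 175 × 2/7 = 50 and 175 × 1/7 = 25, so 50/25/50/50.
- Completers: × 0.8 gives 40/20/40/40, as stated.
- Power: about 0.9999999 for 40 against 20 (noncentral t), consistent with the stated figure above 99%. This point does not change it.

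**4. Scale of the exclusion**

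The documents give no rate. Assuming 1%, 2% or 5% of those randomized are dosed and then discontinued for this reason, 175 × rate = 1.75, 3.5 or 8.75 participants. One participant is 1/50 = 2% of a large arm and 1/25 = 4% of the 100 mg arm.

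**5. Illustration of one exclusion (all event counts assumed)**

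If the excluded participant had the event, k/n becomes (k−1)/(n−1). With no events in 50 on placebo, the two-sided Fisher p-value is C(n,k)/C(n+50,k), doubled when the arms are equal in size so that the opposite table is equally likely. In the other rows the opposite table is more probable than the observed one and is not counted.

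| Arm | Excluded participant | Before | After | p before | p after |
|---|---|---|---|---|---|
| 100 mg | had event | 3/25 (12.0%) | 2/24 (8.3%) | 2300/67525 = 0.034 | 276/2701 = 0.102 |
| 100 mg | no event | 3/25 | 3/24 | 0.034 | 2024/64824 = 0.031 |
| 100 mg | had event | 2/25 | 1/24 | 300/2775 = 0.108 | 24/74 = 0.324 |
| 400 or 800 mg | had event | 6/50 | 5/49 | 0.027 | 0.027 |

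On rates alone in a large arm, 3/50 (6.0%) becomes 2/49 (4.1%). So one exclusion can move a comparison in the smallest arm, and may leave the p-value unchanged in a larger one.

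**The case against.** The case on the other side has several parts.

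- **Reporting rule.** Protocol 9.3.1 lets a non-principal change to analysis methods be described and justified in the CSR. That is right, and a protocol amendment may not be needed. But SAP 4.9 is where the SAP lists such changes, and it describes the EAS change at length while omitting this one.
- **Few or no participants.** Eligibility is confirmed before randomization and first dose, and waivers are not permitted, so the count may be zero. This stands, and limits the size of the problem. The p-value shift also needs the excluded participant to have had the event, and no decision in the documents turns on 0.05 in a safety table.
- **Other outputs show these participants.** SAP 4.2 reports the number dosed by group and the reasons for discontinuation. Appendix 3 covers treatment and study discontinuations, Appendix 5 lists important deviations, and narratives use the randomized population. A gap between the number dosed and the SAS would be visible. The missing events would still not be in the incidence tables.
- **Administrative withdrawal.** Protocol 7.2 allows withdrawal for administrative reasons, which could cover this case and avoid the loss of later visits. The data collected up to withdrawal would still be excluded.
- **Textual basis.** SAP 1.1 equates the safety estimand with the treatment-regimen estimand, whose question concerns effects "in participants who meet the inclusion criteria regardless of treatment discontinuation". That lends the clause some support, but the population bullet under the same estimand is everyone randomized with at least one dose.

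**Conclusion.** The concern holds. The SAS in SAP Section 3 is narrower than the protocol's safety set, through an undefined clause that SAP 4.9 does not declare. Following the SAP as written would leave exposed participants out of the safety tables, although the SAP says safety is assessed irrespective of adherence. The discrepancy is certain, since it rests on the text alone. Its effect is not: it depends on a count the documents do not give, and nothing in them shows whether these participants are at higher risk or whether exclusion would differ by arm. No direction of bias is claimed, and the sample-size figures are unaffected. It should be fixed because the correction is simple and the protocol's definition is clear.

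**What to change.** 1. Delete the inadvertent-enrollment condition from the SAS in SAP Section 3, so that it matches Protocol 9.2.
2. Run the Appendix 7 laboratory safety outputs on the SAS. This agrees with Protocol 9.3.5 and 9.3.5.1, which place laboratory measures among the safety analyses run on the SS. It is more than a change of label: the FAS stops at the treatment period and the SAS adds safety follow-up, so Appendix 7 should state which period its minimum, maximum and last values cover.
3. For the FAS, first reconcile the question and the population bullet of the treatment-regimen estimand in SAP 1.1, then decide whether the clause belongs there.
4. If the clause stays in the FAS or EAS, define inadvertent enrollment, say whether discontinuation is from intervention or from the study, fix the list of affected participants before unblinding, and declare the change in SAP 4.9.

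The cost is one deleted clause, a changed set and stated period in Appendix 7, and one entry in SAP 4.9 if the clause is kept elsewhere. No new data are needed, and the efficacy sets can keep an eligibility restriction if it is declared.
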